## **10 ANALYSIS POPULATIONS**

In pivotal pharmaceutical / therapy studies the general approach is to analyze the intention-to-treat (ITT) population. In such studies the product efficacy and the product

compliance are generally highly correlated as the product effects may be detectable by the subject (e.g., relief from symptoms). Therefore, the ITT population is used to account for the effects of the product compliance. The drivers for product use (ultimately product compliance) for tobacco products are not the same as in a pharmaceutical setting. Smokers decide to smoke, despite the known risks and adverse health effects, based on social, cultural, personal, and psychological factors. Therefore the ITT approach may not be optimal in randomized studies evaluating modified risk tobacco products, as these products are targeting risk reduction which may not be the main factor influencing the choice of tobacco products used by the subjects.

The aim of this study is to demonstrate the optimal effect that could be achieved by the use of THS in terms of reduction in BoExp. The following considerations were taken into account in order to measure “optimal effect” in this study:

1. The primary analysis is designed to assess the effect in subjects who are compliant with the assigned product use, rather than the effect in the full population. The full population would represent a heterogeneous exposure (e.g., as mixed product use, or non-use of the assigned product) rather than a THS exposure.
2. The subjects are allowed to smoke the THS 2.2 Menthol product in a truly *ad libitum* setting (smoking is not restricted based on the number of CC smoked prior to study onset).

The optimal effect may be a somewhat ideal scenario, which differs from the real-world effect (effect under actual use setting) mainly by reducing the impact of non-compliance on the estimate. To be able to assess real-world effects we are planning to conduct studies, both in our clinical program (12 month exposure response studies) and in our perception and behavior program (actual use studies). In order to fully understand the full range of the potential effect THS once it is commercialized it will be important to understand both the optimal effect and the real-world effect.

The PP Set will be the primary analysis for BoExp, and risk markers. The full analysis set (FAS) will be the primary analysis set for compliance to randomization arm. Exposure and questionnaires. Exposure and questionnaires will be described by randomization arm and according to product use categories (see **Table 25**).

A sensitivity analysis will be run on the compliant population for the for BoExp and risk markers.

Safety will be analyzed using the safety population by randomization arm and according to product use categories (see **Table 25**).

### **10.1 Full Analysis Set**

The FAS consists of all the randomized subjects who had at least one post-randomization product use experience, if randomized to THS 2.2 Menthol or mCC, and have at least one valid non-safety assessment (THS 2.2 Menthol, mCC, and SA arms).

### **10.2 Per Protocol Set**

The PP Set is a subset of the FAS and includes all randomized subjects who have no major protocol deviations impacting evaluability as defined in **Table 21** (see Section 11 “Protocol Deviations”).

### **10.3 Safety Population**

Before randomization, the safety population consists of all the subjects who had at least one exposure to THS 2.2 Menthol (including the product test at Admission Day). This also includes any randomized subjects who had no valid safety assessment post-randomization.

After the randomization, the safety population includes all randomized subjects who had at least one valid safety assessment post-randomization. Subjects in the safety populations will be analyzed according to product use categories defined over the whole ambulatory period.

### **10.4 Compliant Population**

The compliant population will be a subset of the PP Set for subjects from the THS 2.2 Menthol arm who are exclusive THS 2.2 Menthol users, as defined in Section 10 “Analysis Populations”, or for subjects from the mCC arm who are exclusive users of mCC, or for subjects in the SA arm who are abstinent, as defined in Section 6.3.3.2 “Abstinence from mCC use”.

## **11 PROTOCOL DEVIATIONS**

Protocol deviations are defined as deviations from any procedure defined in the Study Protocol, including but not limited to any violation of inclusion/exclusion criteria, mis-randomizations, use of any nicotine or tobacco-containing product other than the assigned product during each of the exposure period in confinement, assessments not performed or performed outside the scheduled time windows, or use of drugs that are known to affect CYP2A6 or CYP1A2 activity.

Information following site monitoring and other reviews will be documented in the site visit reports, follow-up letters, audit documentation, or other manual review and subsequently recorded in an electronic data capture (EDC) system. Additional protocol deviations may be identified in the data review, these will also be recorded in the EDC system.

Additional protocol deviations (e.g. time windows for assessments) may be identified through programmatic checks and entered in ADaM datasets.

All deviations will be reviewed to determine their severity/impact when subjects are assigned to analysis populations. Each deviation will be classified as major or minor; all major deviations will be further reviewed to determine whether or not the deviation impacts the evaluability of the results and therefore should result in the subject being excluded from the PP Set.

### 11.1.1 Major Protocol Deviations

Subjects with major protocol deviations will be identified (per period of the study) to determine whether they will be excluded from any of the analysis populations. This will take place during the pre-analysis data review meeting prior to database lock. The following have been identified as the major protocol deviations.

The categories for the major deviations will include, but are not limited to the deviations presented in **Table 21**.

**Table 21: Definition of Major Protocol Deviations**

Category	Description
Mis-randomization	Being administered the wrong product according to the randomization schedule.
Mis-use of product	Confinement: Use of any nicotine or tobacco-containing product other than the assigned product, using the product distribution log. Ambulatory: Non-compliance in the THS 2.2 Menthol and SA arms will be defined for each period. Non-compliance is based on product use reported in the product use diary for periods 2-4, as any of the following occurrences: – Use of more than 2 CC in a single day during the period – Average product use from Day 1 in each period through the end of the period is more than 0.5 CC per day. Violation Duration of 24 hour collection Violation of inclusion/exclusion criteria.
	Start and end times not within the 30 min window.

Among the above criteria, violations of inclusion criteria 1,2,3 and 4, or of the exclusion criteria 2 and 21 will be assessed for their impact on the PP Set. Any violations of other inclusion or exclusion criteria will be assessed for their impact on the PP Set and evaluated during the pre-analysis data review meeting.

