12.1.2 Definitions for Statistical Data Analysis

Baseline:

In general, baseline will be the last available time-point prior to Day 1, 06:30 AM.

THS 2.2 Menthol users:

Subjects switching from mCC to THS 2.2 Menthol whose product use pattern categorization is primarily THS 2.2 Menthol or predominantly THS 2.2 Menthol over a defined period will be considered as THS 2.2 Menthol users during that period. See Section 12.3 for further details on the product use.

Dual use:

Subjects switching from mCC to THS 2.2 Menthol whose product use pattern categorization is dual mostly THS 2.2 Menthol, dual balanced or dual mostly CC over a defined period will be considered as dual users. See Section 12.3 for further details on the product use.

CC users:

Subjects switching from mCC to THS 2.2 Menthol or subjects continuing to use mCC whose product use pattern categorization is primarily CC or predominantly CC over a defined period will be considered as CC users during that period. See Section 12.3 for further details on the product use.

Smoking abstinence:

Data and information contained in this document are considered to constitute trade secrets and confidential commercial information, and the legal protections provided to such trade secrets and confidential information are hereby claimed under the provisions of United States law. No part of this document may be publicly disclosed without the written consent of Philip Morris International.

Smoking abstinence during a defined period is defined as using no tobacco-containing product as reported by the subject on the electronic diary.

Non-compliance to randomization arm:

- **Confinement:**
Use of any nicotine or tobacco-containing product other than the assigned product.
Exhaled CO breath test >10 ppm for subjects from the SA arm
- **Ambulatory:**
Non-compliance in the THS 2.2 Menthol and SA arms will be defined in reference to the time period
 -]Day 6-Day 30 Visit]
 -]Day 30 Visit-Day 60 Visit]
 -]Day 60 Visit-Day 90 Visit]as the use of more than 2 CC during a single day within a time period or the use of on average more than 0.5 CC per day over the exposure study.

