12.4.2 Per Protocol Population

The PP population is a subset of FAS and includes all randomized subjects who

- Have had compliance to their randomized arm (see Section 12.1.2 for the definition of non-compliance to randomized arm).
- Have not been misrandomized, and
- Have no major protocol deviation (to be further described in the SAP).

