		

○ Updated objectives in Section 5.3 to reflect all oxysterols listed in the protocol.

○ Updated Inclusion/Exclusion criteria in Section 6.2 to reflect the text in the protocol.

○ Updated Blinding in Section 6.3.2 to reflect that the study scientist is unblinded for the data review meeting.

○ Abstinence category (100% abstinence) biochemically verified with CO breath test in Section 6.3.3.2. Removed the reference to CEMA study because no longer found to be relevant.

○ Re-organized Section 7.1 in order to concisely describe methods for both urinary BoExp and risk markers. Methods for LLOQ/ULOQ data handling moved in Section 12.1.5.

○ Specified units for Puff number and frequency, and fixed typo in the Average inter puff interval calculation in Section 7.1

○ Included changes from the protocols for Blinding in Section 9.

○ Reworded Analysis population Section 10 in order to clarify the definition of per protocol set which is separately defined on each analysis period (as defined in Section 11.1.1). Clarified that safety populations may be different pre and post randomization, and that product use categories will be defined over the whole ambulatory period.

○ In Section 11.1.1, clarified that:

○ Product compliance will be defined using the product distribution log in confinement and the eDiary in Ambulatory

○ Non compliance is defined for each period

○ The violation of inclusion criteria 1,2,3, and 4 and exclusion criteria 2, and 21 will be interpreted as impacting evaluability, other violations will be interpreted during the data review

○ Included in section 11.1.2 procedural violation category and updated concomitant medication category so to include drugs known to affect 11-DTX-B2 and CYP1A2.

○ Clarified in Section 12.1 that stratified presentation will be performed at period 1 and 4 for the PP set on Baseline characteristics, endpoints for primary objective, and product use.

○ Summarized in Section 12.1.3 the general methods for descriptive statistics of biomarkers and safety data and removed any related text from each endpoint specific section (Section 12.6.1, 12.6.2, 12.6.2.5, and 12.6.4).

○ Listed in Section 12.1.3 the TFL labels used for randomized product use and for stratification factors

○ Clarified the definition of Baseline in Section 12.1.4,

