## **9 CHANGES FROM THE PROTOCOL SPECIFIED STATISTICAL ANALYSIS**

The study team was accidentally unblinded during the course of the study. The first version of the SAP was issued on 30 September 2013 prior to first subject's first visit and shared with the FDA. The list of changes from version 1.0 are listed in section 3.1. The impact of the changes on the interpretation was none and was not influenced by the unblinding.

The blinded review roles were delegated for data review. No decision on populations assignment and data review was made in an unblinded manner.

The analysis of the relationship between primary and secondary BoExp, risk markers, and NEQ is no longer an objective of the study. The impact of the study team being unblinded and making this decision was null.

Urinary BoExp, risk markers, and NEQ will be evaluated using concentration adjusted for creatinine only for the data collected from the 4-hour urine fraction. The impact of the study team being unblinded and making this decision was null.

When investigating the concordance between the results for urinary BoExp, risk markers, and NEQ in 24-hour urine collection and 4-hour urine fraction only the actual value of the concentration adjusted for creatinine will be used. The impact of the study team being unblinded and making this decision was null.

When investigating the urinary BoExp, risk markers, and NEQ in subjects quitting smoking, the 4-hour fraction data will not be used. The impact of the study team being unblinded and making this decision was null.

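### SAP Table 21 leaves out the protocol's exhaled-CO criterion for the SA arm in confinement, Section 9 does not record it, and the secondary Day 5 THS:SA ratios carry a small one-directional risk

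*SAP*

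**What the plan says.** **Protocol.** Section 12.1.2 gives two routes to non-compliance in confinement. One is use of a product other than the assigned one. The other is "Exhaled CO breath test >10 ppm for subjects from the SA arm", with no start day. Section 12.4.2 admits to the PP population only subjects who "Have had compliance to their randomized arm", and refers to 12.1.2 for the definition.

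**SAP, PP rule.** Section 10.2 says the PP Set "includes all randomized subjects who have no major protocol deviations impacting evaluability as defined in" Table 21. The confinement part of the product mis-use row there reads "Use of any nicotine or tobacco-containing product other than the assigned product, using the product distribution log". CO does not appear in it.

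**SAP, role of CO.** Section 6.3.3 says SA compliance in confinement is verified chemically by exhaled CO with a 10 ppm cut-off, and that SA subjects above it are not withdrawn. Section 12.4 makes CO a compliance tool from Day 2 because of carry-over, and plans a summary table. Neither section states a consequence for the PP Set.

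**SAP, record of changes.** Section 9 does not mention the criterion. It says "The list of changes from version 1.0 are listed in section 3.1", and the version 2.0 entry there states "Product compliance will be defined using the product distribution log in confinement and the eDiary in Ambulatory".

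**The concern.** SA subjects are dispensed nothing to smoke after Day 1. A log of dispensed product therefore cannot show a cigarette that an SA subject obtained some other way. Exhaled CO is the objective check for that arm. The protocol ties it to the PP population and the SAP's written PP rule does not.

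The SA arm is the protocol's reference point for the maximum possible exposure reduction (Section 4.2). SAP 12.6.2 plans THS versus SA comparisons of COHb, MHBMA, 3-HPMA and S-PMA on the PP Set. If SA subjects who smoked stay in that set, the SA geometric mean rises and each Day 5 THS:SA ratio falls. The error can go only one way, and that way favours the test product.

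**Working it through.** **1. Side by side.** Protocol PP rule in confinement: non-assigned product use, or (SA arm) CO above 10 ppm. SAP PP rule in confinement: non-assigned product use as shown by the distribution log. The second protocol route has no counterpart in Table 21.

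**2. The plan's own precision figure.** Protocol 12.2 states that the 95% CI limits for THS:SA lie within 18% of the estimate with 80% probability. Inputs are n = 80 and 40, and the THS/SA CVs in protocol Table 19 (SAP Table 16).

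- s = sqrt(ln(1 + CV²)). For S-PMA, CV 0.42 gives s = 0.403.
- Assurance factor = sqrt(χ²₀.₈₀(118)/118) = 1.052, and t₀.₉₇₅(118) = 1.980.
- Upper half-width = exp(1.980 × 0.403 × 1.052 × sqrt(1/80 + 1/40)) − 1 = 17.7%.

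S-PMA has the largest CV. The other three markers give at most 14.7%, so the stated 18% reproduces.

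**3. Level of a smoking SA subject.** mCC:SA = (THS:SA)/(THS:mCC), from the same table:

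- COHb 2.10/0.40 = 5.25
- 3-HPMA 1.70/0.30 = 5.67
- MHBMA 1.00/0.15 = 6.67
- S-PMA 1.15/0.20 = 5.75

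**4. Fall in THS:SA per retained subject.** Let q be the share of the mCC excess still present on Day 5. The subject sits at L = 1 + q(R − 1) times the abstinent level, where R is the mCC:SA ratio. One of 40 such subjects lowers THS:SA by 1 − L^(−1/40).

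Two assumptions are needed: full mCC level at the lapse, and a 24-hour half-life, which is the upper figure in protocol 4.2. A lapse on Day 2 then leaves q = 0.5³ = 0.125, and a lapse on Day 4 leaves q = 0.5. q = 1 means still at full level on Day 5.

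| | COHb | 3-HPMA | MHBMA | S-PMA |
|---|---|---|---|---|
| q = 0.125 | 1.06% | 1.14% | 1.33% | 1.16% |
| q = 0.5 | 2.81% | 2.97% | 3.30% | 3.00% |
| q = 1 | 4.06% | 4.24% | 4.63% | 4.28% |

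**5. How many subjects would matter.** A fall of 18%, equal to the stated precision, needs 40 × ln(1/0.82)/ln(L) subjects. At q = 1 this is 4.8, 4.6, 4.2 and 4.5 of 40 (same order of markers). At q = 0.125 it is 18.6, 17.3, 14.8 and 17.0.

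**6. Precision if the criterion is restored.** With four SA subjects excluded (n = 36), the half-width with 80% assurance goes from 17.7% to 18.4% for S-PMA and from 8.3% to 8.7% for COHb.

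**7. Reach.** The primary model in SAP 12.6.1.1 is specified for THS and mCC data. Day 90 results are not governed by a confinement criterion, because "Subjects with major protocol deviations will be identified (per period of the study").

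**The case against.** The SAP has not abandoned CO, and a reader who inferred that would be wrong. CO is still measured, summarised and called a compliance check. Table 21 is not an exhaustive list, and "all major deviations will be further reviewed to determine whether or not the deviation impacts the evaluability of the results". A data-review meeting could therefore still exclude a CO-positive SA subject. That stands, but it is a case-by-case judgement, whereas the protocol has a fixed rule.

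Site controls also limit the problem. Subjects hand in their cigarettes, each one dispensed is logged, and SA subjects should have no access to the smoking rooms (protocol 6.1.2, 6.5.2.1, 6.6.1.1). Only cigarettes kept back from staff would escape the log, and nothing suggests this would be common. The size estimate is also generous: full mCC level amounts to a day's ordinary smoking, and 24 hours is the upper half-life. All this supports a minor rating.

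It is tempting to say that Section 3.1 hid the change. The documents do not support that. Section 3.1 lists changes from a version 1.0 that is not available here, and it states the log basis openly. The gap in the record is in Section 9.

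It is also tempting to say that no CO-verified THS versus SA analysis exists for the four Day 5 markers. SA members of the Compliant Population must be abstinent as defined in 6.3.3.2, where full abstinence is CO-verified. The Section 3.1 entry on 12.6.1.3 says the compliant-population analysis will cover THS versus SA. Section 12.6.2.1 repeats the sensitivity analyses for the secondary objectives, which include these markers against SA. What remains is that the title of Table 15.2.3.1.3 names mCC only and that of Table 15.2.3.7 refers to additional biomarkers.

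Table 21 is partly scrambled in the available text. Its confinement entry reads as complete.

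**Conclusion.** The discrepancy is real and minor. Followed as written, Table 21 can keep a CO-positive SA subject whom protocol 12.1.2 and 12.4.2 would exclude, and Section 9 does not say so. The secondary Day 5 THS:SA ratios would fall by about 1% to 5% per retained subject of 40, under the two assumptions above. One or two such subjects stay well inside the planned 18% precision, and it would take four or five at full mCC level to match it. The documents give no count, so the total effect cannot be stated.

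Two stronger readings should be resisted. One is that every ratio would move towards abstinence. For COHb, 3-HPMA and S-PMA, planned above 1, a fall does so. MHBMA is planned at 1.00, so its ratio would drop below 1: still favourable to THS, but away from equality with SA. The other is that the study's success criterion is at risk. It rests on THS versus mCC and does not depend on which SA subjects are retained.

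**What to change.** In the confinement part of the Table 21 mis-use row, add exhaled CO above 10 ppm in the SA arm as a named major deviation impacting evaluability for Period 1, applied from Day 2 as in SAP 12.4. Record in Section 9 that the Day 2 start departs from the protocol's undated criterion because of carry-over. If the omission was intended, give the reason in Section 9 instead.

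State how the Day 6 test is handled. It may be done at any time before discharge, whereas the Day 5 urine collection ends at about 06:29 on Day 6 and the COHb endpoint is the Day 5 evening sample. A positive Day 6 result should count only if it can reflect smoking before those samples were completed.

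As housekeeping, align the title of Table 15.2.3.1.3 or 15.2.3.7 with the compliant-population THS versus SA comparison already described in Sections 3.1 and 12.6.2.1.

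The cost is one line, one Section 9 entry and a table title. CO is already measured four times daily on Days 2 to 5 and once on Day 6. A few SA subjects may leave the Period 1 PP Set, with the small loss of precision shown above. No sample size or primary power figure changes.

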- They are several-fold higher in smokers than in smokers abstinent from smoking (Lindner et al., 2011).
- They exhibit, on average, an elimination half-life of \leq 24 hours. Therefore, the 5 days of exposure are sufficient to reach the maximum reduced levels with the THS 2.2 Menthol and SA arms (4 to 5 times the half-life will lead to less than 5% of the original exposure levels of assessed biomarkers on Day 5).

Total NNAL was selected as primary endpoints at Day 90 Visit of THS 2.2 Menthol use as:

- This biomarker is tobacco specific (Goniewicz et al., 2009), and exhibits, on average, an elimination half-life of 10 to 15 days. Therefore, the 91 days of exposure are sufficient to reach the steady state with the THS 2.2 Menthol and SA arms (4 to 5 times the half-life will lead to less than 5% of the original exposure levels on Day 90 Visit).

Some risk markers have been selected in order to evaluate biological changes in THS 2.2 Menthol arm as compared to mCC arm using SA arm as a reference point to verify if the trend of changes upon THS 2.2 Menthol use follow the same trajectory as SA. Among the ones selected, some are well-known to be affected by smoking and to be reversible upon SA as follows:

- CYP1A2 activity, the enzyme which mainly metabolizes caffeine, is decreased as soon as 5 days of SA and after 5 days of use of another candidate MRTP (Faber et al., 2004) and data on file from a previous study (YVD-CS01-EU study).
- 11-DTX-B2 (a major stable metabolite of thromboxane A2, which elicits mainly platelet aggregation) was decreased after 1 week of SA (Benowitz et al., 1993) and after 5 days of use of another candidate MRTP (YVD-CS01-EU study).
- Blood pressure, hs-CRP, fibrinogen, homocysteine, fasting blood glucose, LDL, HDL, TG, TC, hemoglobin A1c (HbA1c), waist circumference, sICAM-1, WBC count, Apo A1, Apo B, and 8-epi-PGF2 α will be evaluated as risk markers (Eliasson et al., 2001; Vasan et al., 2006) for cardiovascular monitoring purposes. According to the literature, some of these risk markers are known to be sensitive to smoking cessation: the levels of HDL increase when the levels of sICAM-1, WBC count, and 8-epi-PGF2 α decrease following 1 to 3 months of smoking cessation (Pilz et al., 2000; Eliasson et al., 2001).

- Body weight as a mean increase of 4.5 kg is observed after 12 months of smoking abstinence with the most weight gain occurring within the first 3 months of quitting (Aubin et al., 2012).

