**Table 25: Stratification Labels**

Stratification Factor	Definition
Product preference (which product the subject would prefer to be randomized to).	THSm2.2 (THS 2.2 Menthol) mCC SA NP (No preference)
Sex	Male Female
Daily mCC consumption (per day)	10-19 >19
Safety Time Periods	Pre-Randomization period ([Product trial – Randomization]) Randomized period Confinement ([Day 1-Day 6 confinement] ) Ambulatory ([Day 6 ambulatory-Day 90 Visit]) Safety Follow-up ([Day 90 Visit – End of Study])
Product Use Time Periods	Period 1 ( [Day 1-Day 6 confinement] ) Period 2 ( [Day 6 ambulatory-Day 30 Visit] ) Period 3 ( ]Day 30 Visit-Day 60 Visit] ) Period 4 ( ]Day 60 Visit-Day 90 Visit] )
Product Use Categories for mCC arm	CC Only (Exclusively CC) CC Dual (Use of other products)
Product Use Categories for SA arm	Abstinent Predominantly Abstinent Not Abstinent
General Product Use Categories for THS 2.2 Menthol arm	THS 2.2 [70-100%] Dual ]30-70%[ CC [0-30%]

PP SetDetailed Product use Categories for THS 2.2 Menthol	Primarily THS 2.2 ([95-100]%) Predominantly THS 2.2 ([70-95]%) Dual Mostly THS 2.2 ([60-70]%) Dual Balanced ([40-60]%) Dual Mostly CC ([30-40]%) Predominantly CC ([5-30]%) Primarily CC ([0-5]%)
---	---

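### Per-period compliance may admit subjects to the Day 90 Total NNAL per-protocol analysis after about 30 compliant days, too short a washout for that marker, and SAP and protocol disagree on the averaging window

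*SAP*

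**What the plan says.** Protocol 4.2 explains why Total NNAL is tested at Day 90 and not Day 5: the marker "exhibits, on average, an elimination half-life of 10 to 15 days", so that "the 91 days of exposure are sufficient to reach the steady state". It adds that "4 to 5 times the half-life will lead to less than 5% of the original exposure levels on Day 90 Visit".

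The SAP's compliance rule works by period. Table 21 says "Non-compliance in the THS 2.2 Menthol and SA arms will be defined for each period", and section 11.1.1 says "Subjects with major protocol deviations will be identified (per period of the study" before the decision on exclusion. Table 25 defines the last interval as "Period 4 ( ]Day 60 Visit-Day 90 Visit". Section 12.1.1 presents PP summaries, including creatinine-adjusted Total NNAL, for periods 1 and 4. Sections 12.3 and 12.5 also treat the PP set as specific to a period, and the revision history describes it that way. Sections 10.2 and 12.6.1.1, which define the set and the primary test, say PP Set without naming a period.

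The two documents differ on the second criterion, an average above 0.5 conventional cigarettes (CC) per day. Protocol 12.1.2 takes the average over the whole exposure. SAP Table 21 counts from a Day 1 that can be read either as the first day of the period or as study Day 1. SAP section 9, which lists changes from the protocol, does not mention this rule.

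**The concern.** The per-period rule suits the four Day 5 primary markers, whose half-lives are at most about 24 hours. Total NNAL carries a longer memory. If PP membership at Day 90 looks back only to the Day 60 Visit, a subject who smoked through periods 2 and 3 and then complied enters the analysis with NNAL that still reflects the earlier smoking.

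SAP section 10 states the target: "The aim of this study is to demonstrate the optimal effect that could be achieved by the use of THS". Late compliers blur it in two ways.

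- **THS against mCC (primary).** Carry-over raises NNAL in the THS arm, moves the ratio toward 0.50 and lowers power.
- **THS against SA (SAP 12.6.2, PP set).** Carry-over in the SA arm raises the abstinence reference, so THS looks closer to abstinence than it is.

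The other planned analyses do not guarantee a set of sustained compliers. The mixed-model analysis stays in the PP set, the compliant population is a subset of it with no look-back period stated, and the FAS analysis adds non-compliers.

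**Working it through.** **Inputs.** Half-life 10 to 15 days (protocol 4.2). Period 4: nominally 30 days (SAP Table 25). Visit window: ±5 days relative to the previous visit (protocol 9.3), so 25 to 35 days. NNAL mean ratio 0.30, CV 0.60 (SAP Table 17). Sample size 40:40 for NNAL and 80:40 for the Day 5 markers (SAP Table 19). Margin 0.50, one-sided 2.5%.

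**Step 1: the plan's own power.** SD on the log scale = sqrt(ln(1 + CV²)). Power = Φ(ln(0.50/ratio)/SE − 1.96). For NNAL: SD = sqrt(ln 1.36) = 0.555; SE = 0.555 × sqrt(1/40 + 1/40) = 0.124; ln(0.50/0.30) = 0.511; power 98.5%. The product over the five markers is 94.3% and 98.2% under the two sets of assumptions, matching the 94% and 98% in the 50% column of SAP Table 20. The columns for larger reductions do not all reproduce with this simple product; they are not used here.

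**Step 2: carry-over.** Residual = 0.5^(days/half-life).

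| Compliant days | Half-life 10 d | Half-life 15 d |
|---|---|---|
| 25 | 17.7% | 31.5% |
| 30 | 12.5% | 25.0% |
| 35 | 8.8% | 19.8% |
| 85 (periods 2 to 4) | 0.3% | 2.0% |
| 91 | 0.2% | 1.5% |

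Falling below 5% takes ln(20)/ln(2) = 4.32 half-lives, or 43 to 65 days. Period 4 is too short at either half-life.

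**Step 3: level of a late switcher.** Assume smoking at the mCC level to Day 60, then THS only. Level = 0.30 + 0.70 × residual: 0.39 at 12.5% and 0.475 at 25%, against the planned 0.30.

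**Step 4: illustrative NNAL power at 40:40.** A share p of the 40 THS subjects are late switchers at level L. Geometric mean ratio = 0.30^(1−p) × L^p; THS variance = SD² + p(1−p)(ln(L/0.30))². The share is an assumption.

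| Share p | Half-life 10 d | Half-life 15 d |
|---|---|---|
| 0 | 98.5% | 98.5% |
| 10% | 97.3% | 95.8% |
| 25% | 94.6% | 87.2% |
| 50% | 86.2% | 58.5% |

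**Step 5: the protocol's averaging rule.** A limit of 0.5 CC per day over 85 to 91 days allows 42.5 to 45.5 CC in total. A subject at the entry minimum of 10 per day from Day 6 to Day 60 smokes 54 × 10 = 540, or 540/90 = 6 per day. Even 1 per day over those 54 days exceeds the limit. On this rule regular smokers in periods 2 and 3 are out, and the problem largely disappears.

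**The case against.** The strongest reply is that a Day 90 PP set resting on period 4 alone is an inference. No sentence assigns that set to the NNAL test, and section 12.1.1 governs stratified summaries. The SAP is written to supplement the protocol and announces no departure from its averaging rule, under which Step 5 removes most of the difficulty. This stands, and it is why the point concerns an unreconciled rule. It does not dispose of it: Table 21 can be read by period, and the surrounding sections favour that reading.

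Four stronger readings are tempting, and the documents do not support them.

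- **False success on the primary test.** Carry-over raises NNAL in the THS arm, so it works against showing a 50% reduction.
- **Late compliers would measure at 12.5% to 25% of their earlier level.** Those figures are carry-over only; with THS use at the plan's ratio the level is about 39% to 47.5%.
- **The visit windows shorten period 4 to 20 days.** Protocol 9.3 ties the window to the previous visit, which gives 25 to 35 days.
- **A firm figure for the SA bias.** SAP Table 16 gives no NNAL value against SA, and neither document gives a background level or a share of late quitters.

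It is also fair to say that the Table 21 list is open-ended and evaluability is judged at the pre-analysis review. That could catch such subjects but does not commit anyone to do so.

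**Conclusion.** The concern holds as a gap between two rules, and it should be closed. On the natural reading of the SAP, subjects can enter the Day 90 Total NNAL analyses after 2 to 3 half-lives of compliance (at 30 days), with 12.5% to 25% carry-over, or 8.8% to 31.5% across the visit window. The protocol's rationale relies on under 5%. On the protocol's averaging rule the gap largely closes, but the SAP does not say that this rule applies.

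For the primary comparison the consequence is a diluted effect and some lost power. The power figures in Step 4 assume full mCC-level smoking to Day 60, abrupt compliance afterwards and a share of late compliers that the documents do not give, so they show sensitivity and are not a forecast. For THS against SA, carry-over in the SA arm favours the product. A given residual is a larger fraction of a lower level, but the net effect depends on how many late compliers each arm has, which is unknown. The Day 5 markers are not affected.

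**What to change.** 1. Reconcile SAP Table 21 with protocol 12.1.2. State the window over which the 0.5 CC per day average is taken, and the period or periods whose compliance defines the PP set for Day 90 Total NNAL. If the SAP departs from the protocol, list that in section 9.
2. Pre-specify a sensitivity analysis of Day 90 Total NNAL, THS:mCC and THS:SA, in subjects compliant in all of periods 2 to 4. Over about 85 days the residual is 0.3% to 2.0%. With every visit at its earliest (19 + 25 + 25 = 69 days) it is at most 0.5^(69/15) = 4.1%, still under 5%. Requiring only periods 3 and 4 would not be enough: 60 days at a 15-day half-life leaves 0.5^4 = 6.25%.
3. Keep the per-period rule for the short half-life markers.

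The cost is SAP wording and one more table; the daily product-use diary already holds the data. The set will be smaller by an unknown amount. On the plan's inputs, NNAL power is about 96% to 97% with 30 THS subjects against 40 mCC, and 92% with 20 against 40.
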